## 5.5.1 Subject Capacity

We anticipate that all subjects will have the capacity to provide informed consent. Patients who are not able to consent will not be included in the study.

### 5.5.2 Subject/Representative Comprehension

CHWs will use the "teach back" method  $^{\rm 45}$  to assess subject comprehension of the potential risks and benefits of study participation.

## 5.6 Informed Consent

The PI will be responsible for ensuring that valid consent is obtained and documented for all subjects unless the IRB waives the requirement for documentation of informed consent for all or part of the study

### 5.6.1 Process of Consent

CHWs will obtain consent from each subject. The consent will be obtained during CHW visit for health care, either at the patient's residence or the clinical meeting site for their community. Consent forms will be translated into Spanish by [name], who is fluent in Guatemalan Spanish and has been certified to see Spanish-speaking patients independently by UW Interpreter Services. Consent discussion will primarily occur in Spanish. Most patients speak Spanish and Kaqchikel, a Mayan language, so some part of the consent discussion may occur in Kaqchikel as all CHWs are bilingual Spanish and Kaqchikel speaking. Most CHWs and patients are not literate in Kaqchikel, only Spanish, so the consent form will not be translated into Kaqchikel.

The amount of time given for the consent discussion will take approximately ten minutes but may last as long as necessary to ensure patient understanding of the study. The participant will be given as much time as needed to make a decision. All staff will undergo project specific training that includes methods of obtaining consent. These methods include thorough explanation of the study, risks and benefits of participation, emphasis of voluntary participation and withdrawal at any time, assurance that non-participation will not affect health care and provision of adequate time for independent decision.

Consent will be documented on paper forms, which will be stored in a locked receptacle either at SLMH or at the CHW headquarters in the village of Quixaya.

# 5.6.2 Consent Form (see templates for UW-Madison)

See in ARROW

# 5.6.3 HIPAA

Information about study subjects will be kept confidential and managed according to the requirements of the Health Insurance Portability and Accountability Act of 1996 (HIPAA). Attached/submitted as part of our application is a signed subject authorization form that includes:

- The collection of the following protected health information (PHI)
  - o Identifying information: name, date of birth, community
  - Past medical history and current medical problems
  - Your treatment for diabetes
  - o Measurements: height, weight, waist circumference, vital signs
  - Lab results, including blood glucose and hemoglobin A1c
  - Information about symptoms and medical problems related to diabetes

[name]

- Access of this information by CHWs to provide diabetes care and carry out the program, SLMH Medical Director [name] to provide supervision of CHWs and oversight of treatment decisions, by the study investigators to supervise the study and analyze program efficacy and study results, and by the IRB for study monitoring and supervision.
- The patient can revoke their authorization if they decide to withdraw from the study

### 5.6.4 Revoking Consent

In the event that a subject revokes authorization to collect or use PHI, the investigator, by regulation, retains the ability to use all information collected prior to the revocation of subject authorization. For subjects that have revoked authorization to collect or use PHI, attempts will be made to obtain permission to collect at least vital status (i.e. that the subject is alive) at the end of their scheduled study period.

### 5.6.5 Costs to the Subject

The cost of study medications used in the program, POC and other lab testing and supplies, CHW labor costs, emergency transport of patients to SLMH as needed, and treatment of adverse effects from study medication (e.g. hypoglycemia) will be covered by funding from a Global Health Seed Grant from the UW Global Health Institute. In general, care provided at SLMH is free or very low cost, but patients may be responsible for the cost of care provided outside of the study protocols (payment for this care will not come from study grant funding).

# 5.6.6 Payment for Participation

Patients will receive free diabetes care through the study program, including medications, testing, emergency transportation to SLMH, and treatment of medication adverse effects as needed. There will be no additional compensation.

## 5.7 Early Withdrawal of Subjects

#### 5.7.1 Premature termination of study

This study may be temporarily suspended or prematurely terminated if there is sufficient reasonable cause. Written notification, documenting the reason for study suspension or termination, will be provided by the PI or co-investigator to the IRB. If the study is prematurely terminated or suspended, the PI will promptly inform the IRB and will provide the reason(s) for the termination or suspension.

Circumstances that may warrant termination or suspension include, but are not limited to:

- Determination of unexpected, significant, or unacceptable risk to participants
- Demonstration of efficacy that would warrant stopping
- Insufficient compliance to protocol requirements
- Data that are not sufficiently complete and/or evaluable
- Determination of futility

Study may resume once concerns about safety, protocol compliance, data quality are addressed and satisfy the IRB.

## 5.7.2 When and How to Withdraw Subjects

Subjects may be withdrawn from the study in the following scenarios: • Subject consent withdrawal

Version #: 1.0

[name]

- Subject becomes pregnant
- Subject unable to take metformin or glibenclamide due to adverse effects or development of severe renal dysfunction (eGFR <30mL/min/173 m^2)
- Subject requires insulin or other alternative treatment for diabetes
- Clinical discretion of the site medical director, [name]

When subjects are withdrawn from the study, they will be promptly referred to [name] at SLMH for continuing diabetes and other appropriate medical care.

### 5.7.3 Data Collection and Follow-up for Withdrawn Subjects

Data collected prior to withdrawal will be included in the study.

# 6 Study Agent

### 6.1 Description and Formulation

In this study, we will be using a smartphone application which we designed to guide CHWs through the clinical assessment of patients with diabetes including collection of demographic data and past medical history, assessment of medication history, adherence, and adverse effects, measurement of glycemic control, screening for complications, medication administration and titration, and patient counseling. This application will run in the web-browser of an Android smartphone. This application is IDE exempt.

The medications we will be using are as follows:

- Metformin HCl regular-release 850 mg tablets
- Glibenclamide (glyburide) regular-release 5 mg tablets
- Aspirin 81 mg tablets

# 6.2 Packaging

Metformin and glibenclamide come in blister packages of 10 tablets each. Aspirin comes in a bottle.

### 6.3 Preparation, Administration and Storage of Study Drug

No preparation of the study drugs is necessary. They will be stored in a storage locker at the CHW headquarters in Quixaya, San Lucas Tolimán, Guatemala.

## 6.4 Route of Administration

All medications are administered by mouth. Patients will be treated with at least one of the three medications during the entire duration of the study and their participation in the diabetes treatment program (so, at least 6 months), aside from patients who may be observed off of medication to see if their diabetes is diet-controlled. Whether a patient is taking one of these medications or not depends on their individual characteristics, including glycemic control and targets, experience of side effects, and medication adherence, as described by the treatment protocols outlined below and in the appendices.

# 6.5 Starting Dose and Dose Escalation Schedule

Metformin will be started at 850 mg once daily and increased to the target dose of 1700 mg after 2 weeks. If not meeting treatment goals after ≥1 month, metformin can be increased to 2550 mg. Patients who are unable to tolerate the 1700 mg dose will take the 850 mg dose.

Version #: 1.0

[name]

Glibenclamide will be used for patients who are unable to tolerate metformin, in addition to metformin if A1c  $\geq$ 9, or if glycemic goals not met despite maximal dose of metformin. Dosing will start at 2.5 mg once per day. If glycemic goals are not met after  $\geq$ 1 month, dose will be escalated to 5 mg once per day and then 10 mg once per day as needed.

Aspirin will be dosed at 81 mg once per day for secondary prevention in eligible patients with history of MI or stroke or patients who have new chest pain and are awaiting medical workup for possible CAD. Patients with high risk chest pain and possible ACS will be treated with aspirin 324 mg (four 81 mg tablets) once while awaiting emergency transport to SLMH.

Please consult Appendix 8, Appendix 10, and Appendix 11 for further information on medication titration protocols

# 6.6 Dose Adjustments/Modifications/Delays

See 6.5 above and relevant appendices

### 6.7 Prior and Concomitant Therapy/ Standard of Care

Some patients may already be taking metformin and/or glibenclamide prior to enrollment. Their doses will be adjusted based on glycemic goals, current control, medication adherence, and medication side effects. Patients may require additional medication therapy or other treatment for complications of diabetes or other health problems while they are participating in the study. The only medication that would preclude them from further participation in the study would be if they needed to start insulin for uncontrolled diabetes or emergence of a contraindication to metformin or glibenclamide.

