## [name]

recommendations are given in every case), training of CHWs and physician oversight of application treatment recommendations and CHW decisions regarding medication administration and referrals.

Exit criteria for the study includes the following:

- Patient with eGFR <30 mL/min will be unable to safely take metformin or glibenclamide and thus will be
  excluded from the program. These patients will be referred to San Lucas Mission Hospital (SLMH) for
  consultation with [name] regarding alternate medication therapy.

- Women who are found to be pregnant during the study
- Patients who require insulin or additional medication other than metformin or glibenclamide for diabetes control

Patients with mild adverse effects, such as gastrointestinal upset from metformin or mild hypoglycemia or hypoglycemia symptoms on glibenclamide will have their medication adjusted according to the titration algorithms used by the application. Patients who are unable to tolerate metformin or glibenclamide due to adverse effects will be referred to [name] for assessment and further treatment recommendations. Patients with more severe adverse effects, such as severe hypoglycemia (defined as resulting in alteration in mental status and requiring assistance from a CHW) or hypoglycemia not responsive to initial measures in the field will be transferred to SLMH via ambulance for further care.

The program will pay the costs related to ambulance transfer to SLMH and the cost of treatment for medication adverse effects. Patients may incur costs from treatment for other complications of diabetes that fall outside the scope of the program, though this care is highly subsidized through the SLMH.

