### 9.2.2.1 Missing Data

The smartphone application will assist in ensuring complete data entry in that most fields are required before the CHW can proceed to the next section of the visit and most data is entered through the use of radio buttons, prepopulated list options, and parameter-limited text boxes. Retention and follow up of patients will be enhanced by visiting patients who miss monthly group visits at their homes. Only patients who completed follow up to each relevant time point (e.g. 6 months, 12 months) will be included in these analyses.

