# Indications for referrals

- Routine referrals
  - Stage I hypertension (BP 140-160/90-100 mmHg)
  - Non-infected diabetic ulcer
  - Need for renal function testing
  - A1c ≥9 despite maximal doses of metformin and glibenclamide for ≥3 months
  - A1c ≥9 for 3 consecutive checks
  - A1c above glycemic target, but less than 9 for 4 consecutive checks
  - Recent chest pain, moderate risk (2 of 5 points)
  - Blood in stool or possible melena
  - $\circ$   $\;$  Patient has other symptoms not addressed by the program protocols
  - Urgent referrals
    - Stage II hypertension (BP 160-200/100-120 mmHg)
    - Possibly infected diabetic ulcer, no signs of systemic infection
    - Worsening vision
    - FBG detectable, but ≥400
    - o A1c ≥14
    - Patient cannot tolerate minimum doses of metformin and/or glibenclamide
    - Current chest pain, moderate risk (2 of 5 points)
  - Emergency referrals
    - Severe hypertension (BP ≥200/120 mmHg)
    - Fasting blood glucose undetectable high
    - Postprandial/random blood glucose undetectable high with mental status changes
    - Hypoglycemia associated with altered mental status
    - Persistent hypoglycemia despite treatment in the field
    - Current chest pain, high risk (≥3 of 5 points)
    - o Possibly infected diabetic ulcer with signs of systemic infection

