    - c. Glibenclamide 10 mg  $\rightarrow$  metformin 1700 mg + glibenclamide 5 mg
    - d. Glibenclamide 15-20 mg  $\rightarrow$  metformin 1700 mg + glibenclamide 10 mg
- 10. Taking glibenclamide with hypoglycemia or hypoglycemia symptoms, previous problems with metformin a. Agrees to take metformin
  - i. Glibenclamide 2.5 mg  $\rightarrow$  metformin 850 mg
    - ii. Glibenclamide 5 mg  $\rightarrow$  metformin 850 mg + glibenclamide 2.5 mg
    - iii. Glibenclamide 10 mg  $\rightarrow$  metformin 850 mg + glibenclamide 5 mg
    - iv. Glibenclamide 15-20 mg  $\rightarrow$  metformin 850 mg + glibenclamide 10 mg
- Version #: 1.0

[name]

- b. Refuses to take metformin
  - i. Glibenclamide 2.5 mg  $\rightarrow$  MD consult
  - ii. Glibenclamide 5 mg  $\rightarrow$  glibenclamide 2.5 mg
  - iii. Glibenclamide 10 mg  $\rightarrow$  glibenclamide 5 mg
  - iv. Glibenclamide 15-20 mg  $\rightarrow$  glibenclamide 10 mg
- 11. Taking metformin and glibenclamide without problems
  - a. Metformin 500-1000 mg + glibenclamide 2.5-10 mg → metformin 1700 mg + current glibenclamide dose
  - b. Metformin 500-1000 mg + glibenclamide 15-20 mg → metformin 1700 mg + glibenclamide 10 mg
  - c. Metformin 1500-2000 mg + glibenclamide 2.5-10 mg  $\rightarrow$  metformin 2550 mg + glibenclamide current dose
  - d. Metformin 1500-2000 mg + glibenclamide 15-20 mg  $\rightarrow$  metformin 2550 mg + glibenclamide current dose
  - e. Metformin 2550 mg + glibenclamide 2.5-10 mg → metformin 2550 mg + glibenclamide current dose
  - f. Metformin 2550 mg + glibenclamide 15-20 mg  $\rightarrow$  metformin 2550 mg + glibenclamide 10 mg
- 12. Taking metformin and glibenclamide, problems with metformin
  - a. Agrees to take metformin
    - i. Metformin 500-850 mg + glibenclamide 2.5 mg  $\rightarrow$  metformin 850 mg + glibenclamide 5 mg
    - ii. Metformin 500-850 mg + glibenclamide 5 mg  $\rightarrow$  metformin 850 mg + glibenclamide 10 mg
    - iii. Metformin 500-850 mg + glibenclamide 10-20 mg → metformin 850 mg + glibenclamide 10 mg
  - b. Refuses to take metformin
    - i. Metformin 500-850 mg + glibenclamide 2.5 mg  $\rightarrow$  glibenclamide 5 mg
    - ii. Metformin 500-850 mg + glibenclamide 5 mg  $\rightarrow$  glibenclamide 10 mg
    - iii. Metformin 500-850 mg + glibenclamide 10-20 mg  $\rightarrow$  glibenclamide 10 mg
  - c. Metformin 1000-1700 mg + glibenclamide 2.5 mg  $\rightarrow$  metformin 850 mg + glibenclamide 5 mg

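### Section 6.7 contradicts the section 2.7.2 exit criterion for a non-insulin add-on drug, and another diabetes drug recorded at entry triggers no stop or consult before glibenclamide is recommended

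*Combined protocol and SAP*

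**What the plan says.** **Leaving the study.** The exit criteria at the end of section 2.7.2 include "Patients who require insulin or additional medication other than metformin or glibenclamide" for diabetes control. Section 5.7.2 opens its list with "Subjects may be withdrawn from the study in the following scenarios", and one item is "Subject requires insulin or other alternative treatment for diabetes". Section 6.7 states: "The only medication that would preclude them from further participation in the study would be if they needed to start insulin for uncontrolled diabetes". That sentence goes on to add one further ground, a contraindication to metformin or glibenclamide.

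**Analysis.** Section 5.7.3 says "Data collected prior to withdrawal will be included in the study". Section 9.2.2.1 says "Only patients who completed follow up to each relevant time point (e.g. 6 months, 12 months) will be included in these analyses".

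**Entry.** Among diabetes drugs, only insulin is an exclusion (section 5.3) and a hard stop in the screening questions (Appendix 1). Appendix 3 then asks about any other prescribed diabetes drug. A positive answer leads the community health worker (CHW) to enter its name, strength and daily pill count, and it opens the general side-effect questions.

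**The concern.** Patients who fail maximal oral therapy are the ones most likely to be offered a third drug, and they are by definition poorly controlled. Under 2.7.2 they leave; under 6.7 they stay unless the drug is insulin. In a completer analysis that choice decides whether their follow-up A1c counts. Removing them would tend to make both primary endpoints look better. Keeping them mixes in the effect of a drug outside the algorithm. Either policy can be defended, but the protocol should hold only one.

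The entry question raises a safety issue. Section 2.7.1 names glibenclamide as the study drug with the highest potential for harm, mainly through hypoglycemia. The application can learn that a patient already takes another insulin secretagogue and still recommend glibenclamide at the same visit, with no prompt to ask anyone first.

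**Working it through.** The plan gives no figure on this point, so the check is a comparison of the text and a trace through the application.

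**1. The rule for a patient who needs a non-insulin third drug**

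| Section | Drugs covered | Force | Result |
|---|---|---|---|
| 2.7.2 | insulin or any additional diabetes drug | exit criterion, no discretion stated | leaves |
| 5.7.2 | insulin or an alternative treatment | *may*, heading the whole list | points to leaving |
| 6.7 | insulin only | categorical | stays |

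The conflict is between 2.7.2 and 6.7.

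**2. Effect on the analysis.** Section 8.2 specifies paired t tests and the McNemar test. Both need a baseline and a follow-up value from the same patient. Section 5.7.3 keeps what was collected before withdrawal, but a patient who leaves before month 6 has no 6-month value and falls out under 9.2.2.1.

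**3. Whether this can reach the 6-month analysis.** Appendix 7 sends patients to the medical director for "A1c ≥9 despite maximal doses of metformin and glibenclamide for ≥3 months". In the Appendix 8 block for A1c 9 to 14, row 11c covers "Metformin 1500-2000 mg + glibenclamide 2.5-10 mg". It raises metformin to 2550 mg and leaves glibenclamide where it was, so it produces maximal doses of both drugs (2550 mg and 10 mg) only for a patient already on glibenclamide 10 mg. For that patient, month 0 plus 3 months is the month-3 visit, before the 6-month endpoint. The referral is a routine one. A third drug must then be prescribed and an exit rule applied before the analysis set changes.

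**4. Where the other-drug answer goes**
- Appendix 1 screening: only insulin stops the application.
- Appendix 3: the answer is stored, with no stop and no consult.
- Appendix 7: no referral indication mentions another diabetes drug.
- Appendices 8, 10 and 11: rows are defined by metformin, glibenclamide, tolerance, adherence, hypoglycemia, and glucose or A1c. None uses the answer.
- Nowhere is there a rule to stop, continue or review the other drug.

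**5. Worked case.** Take a patient on metformin 500 to 2000 mg, tolerated, plus another secretagogue, with A1c between 9 and 14. Appendix 8 row 5a of that block gives metformin 1700 mg with glibenclamide 2.5 mg. Appendix 4 puts the hypoglycemia symptom list only to patients taking glibenclamide, so this patient is not asked it at that visit. Once on glibenclamide, the patient is asked at later visits. A user of another secretagogue who never starts glibenclamide is not asked at all.

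**The case against.** **On the exit rule.** A reader might infer that the three sections set three separate rules. The documents do not support that. The *may* in 5.7.2 heads a list that also contains consent withdrawal and pregnancy, and section 10.4.5 has a patient with a positive pregnancy test withdrawn outright. The word is therefore weak evidence of a distinct discretionary policy, and 5.7.2 points the same way as 2.7.2. It can also be said that the sentence before the quoted one in 6.7 concerns treatment for complications and other health problems, so the remark may have been aimed at concomitant drugs generally. That softens the conflict but does not remove it: the wording is categorical, and it names a diabetes drug.

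**On dosing.** A reader might infer that the algorithm instructs CHWs to stack two secretagogues. No row says so. The application outputs a recommended regimen, and some rows plainly replace a drug: at A1c 6.5 to goal, row 6a moves a glibenclamide user to metformin alone. What stands is that no row stops or continues a third drug, so nothing prevents the patient from taking both. Such a patient is arguably outside the scope of Appendix 8, and section 2.1 offers telephone advice for such situations. That call depends on the CHW recognising the problem.

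**Safeguards.** Coordinators accompany CHWs for the first several months, glucose is tested at every visit with a protocol for readings below 70, Appendix 9 provides hypoglycemia teaching, the unscheduled-visit module covers hypoglycemia, and 2.5 mg is the lowest dose. These reduce the risk. None is a stop tied to the recorded drug, and scheduled physician review may come up to 1 week after the visit.

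**Conclusion.** Both parts hold, and both are minor. Sections 2.7.2 and 6.7 give opposite answers for a non-insulin add-on drug, and the other-drug answer at entry feeds no stop, consult, referral or dosing row.

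Neither part can be sized. The documents give no rate of third-drug use, so the number of patients affected and the amount of bias cannot be derived. The expected direction, flattering results if these patients are removed, assumes that they would have had higher A1c at follow-up than those who stay. A reader might also infer that the 6-month result is broadly exposed through early referral. The row 11c route does not show that, because it applies only to patients already on glibenclamide 10 mg at entry and needs several further steps.

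Patients on another secretagogue are probably uncommon. Sections 2.6 and 2.7.1 describe other sulfonylureas as hard to obtain or too costly locally, and section 7.2 describes clinics that dispense metformin and glibenclamide. They are not excluded, however, and Appendix 1 lists outside sources of diagnosis such as the social security service and private doctors. Counting the Appendix 8 rows that start glibenclamide would not give a risk, since rows are not patients.

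**What to change.** **Exit rule.** Amend the sentence in 6.7 to match 2.7.2, so that needing insulin or any diabetes drug other than metformin or glibenclamide ends participation. Use the same wording for the item in 5.7.2. Report at 6 and at 12 months how many patients left under this rule. The cost is a wording change in two sections and one added line in each report. It gives up the option of keeping such a patient and loses that patient's later A1c, which is why the count should be reported.

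**Entry.** When the Appendix 3 answer on other diabetes medication is positive, require a coordinator or medical director consult before dispensing, as Appendices 8 and 11 already do for A1c above 14. The consult can then settle whether the other drug is stopped. Ask these patients the Appendix 4 symptom questions as well. The cost is one application branch on a field already collected and a short dispensing delay for those patients only. Section 2.7.1 rejected prior physician approval on logistic grounds as a general requirement; a consult limited to flagged patients is a much smaller burden.
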